15.3 Sample Size Considerations

A formal sample size calculation is not applicable for the proposed study. However, at least 50 subjects across more than 5-10 institutions may receive terlipressin treatment during the course of the intervention portion of the study. For the comparison of the terlipressin treatment group and retrospective controls, we expect to have 50 subjects in the intervention group and 150 subjects, assembled from the study sites, in the control group. Assuming a type 1 error of 0.05 and power of 80%, we expect to be able to detect a range of differences in serum creatinine (SCr) depending on the standard deviation of the change (primary endpoint) expected for the groups (see below). Based on results from the REVERSE trial, a change in SCr of as small as 0.05 mg/dL would be able to be detected if the standard deviation for the change approximated 0.10 mg/dL and a pre-specified sample size of 200 subjects, 50 of whom are in the intervention arm, is used for the calculation.

	Δ SCr mg/dL				
Detectable Difference	0.46	0.34	0.23	0.11	0.05
Standard Deviation	1.00	0.75	0.50	0.20	0.10

Given the relatively small number of subjects proposed for inclusion in this terlipressin study, we will likely be underpowered to detect a difference in the other secondary outcomes being explored.

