3.5.2 M&O Off-Label Use

The combination of midodrine/octreotide (M&O), in conjunction with albumin, has been used “off-label” in the United States for treatment of HRS Type 1 for years. Small studies, mostly single center, have demonstrated favorable outcomes for M&O in treatment of HRS Type 1 (Angeli, 1999; Wong, 2004; Esrailian, 2007). The use of M&O plus albumin is recommended in the 2012 AASLD guidelines for the treatment of HRS Type 1 (Runyon, 2013), particularly in light of the fact that terlipressin was not available in the United States at the time of publication. However, the largest multi-centered study comparing terlipressin to M&O undertaken by the Italian Association for the Study of the Liver Study Group on Hepatorenal Syndrome, was stopped early due to the considerable differences in HRS reversal between terlipressin and M&O (55.5 vs 4.8%, p<0.001) (Cavallin, 2015).

Midodrine/Octreotide use in patients on the liver transplant wait list with HRS Type 1

Increasing the duration of time in which a patient with decompensated cirrhosis experiences renal dysfunction decreases the likelihood of renal recovery after liver transplant (Campbell, 2005). Wong et al retrospectively evaluated patients that had experienced HRS Type 1 without reversal prior to liver transplant at University of Toronto between 2001 to 2010 (n=62); M&O was used as treatment of HRS Type 1 in the majority of these patients (Wong, 2015). While none of the patients in the cohort had HRS reversal, 76% were free from dialysis 30 days after liver transplant and had a serum creatinine ≤ 1.5 mg/dL (Wong, 2015). The duration of HRS type 1 and the number of dialysis days prior to liver transplant were highly predictive of post-transplant renal function (Wong, 2015). Additionally, those patients that were not dialysis-free 30 days post-transplant with serum creatinine ≤ 1.5 mg/dL had higher mortality rates (Wong, 2015). This data suggests that even if HRS reversal is not possible, that limiting the dialysis days and length of HRS type 1 can lead improve renal outcomes post-transplant.

4 Study Rationale

The purpose of this open labeled study is to assess safety/efficacy for continuous terlipressin infusion in liver transplant-eligible adult subjects with Hepatorenal syndrome- Acute Kidney Injury (HRS-AKI).

5 Safety and Efficacy Assessments

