6.1 Overall Study Design and Plan: Description

Prospective Terlipressin Group

This is a collaborative open-label, multicenter study of terlipressin infusion following an initial bolus dose of 0.5mg. Written informed consent will be obtained by the investigator, sub-investigator, or qualified designee from the subject or legally authorized representative (LAR) prior to the subject enrollment into the study. Approximately 50 subjects are planned to be enrolled at 5-10 sites in the US. Subjects will receive up to 14 days of terlipressin treatment.

Retrospective Control Group

This study will also seek clinical data from a Retrospective Control Group of patients who would have met inclusion/exclusion criteria detailed below and received at least 48 hours of treatment with Midodrine and Octreotide (M&O), albumin, or other vasopressor used for the treatment of HRS-AKI. Retrospective cases collected from each site should include eligible patients starting from prior to site IRB approval for this protocol and going back to January 2015. Subjects enrolled in a blinded clinical trial in this time period are excluded.

7 Study Population

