15.1 Primary Analysis

The primary analysis will utilize mixed effects regression modeling to estimate changes in serum creatinine (SCr) over the study period, accounting for baseline SCr and the correlation structure between the repeated measures. All potential confounders will be added to the model and sequentially removed if they do not confound the association between receipt of terlipressin and improvement in Scr. Those confounders resulting in a $\geq 10\%$ change in the coefficient for the association between terlipressin and improvement in SCr will be retained in the final model. For all generated models, Aikaike Information Criteria (AIC) scores will be calculated and compared. The model with the smallest absolute AIC value will be accepted as the most parsimonious and will be used as the primary model for the explanation of study results. As has been undertaken in other terlipressin studies in HRS, a least-squares means analysis will be conducted using a repeated-measures analysis of variance. The results from this approach to the statistical analysis can then be directly compared to prior study results.

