15.2 Secondary Analyses

A number of secondary outcomes will be examined for the study cohort. These outcomes include the incidence of dialysis, mortality, and liver transplantation at day 30 and 90. The

incidence of kidney transplant within one year of liver transplant will also be determined. Additionally, descriptive comparisons of SCr will be undertaken at day 30 and 90 of follow up and at 4 time points after receipt of liver transplantation (day 30, 90, 180 and 365) and also at similar time points for those patients who were transplant ineligible or did not undergo a transplant. Incidence will be calculated as the number of new events during the observation period divided by the total persons at risk. All statistical analyses will be conducted using Stata version 15.1 statistical software (StataCorp, College Park, TX). Statistical significance will be declared for a two-sided hypothesis test if the *P* value was <0.05.

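### Section 15.1 makes no allowance for unequal spread of SCr change in 50 terlipressin and 150 control patients; robust or group-specific variances would protect interval coverage at almost no cost

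*Combined protocol and SAP*

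**What the plan says.** Section 15.3 states that "we expect to have 50 subjects in the intervention group and 150 subjects, assembled from the study sites, in the control group". Its conditions are "Assuming a type 1 error of 0.05 and power of 80" per cent, and 15.2 adds "Statistical significance will be declared for a two-sided hypothesis test". The detectable SCr difference is said to vary "depending on the standard deviation of the change (primary endpoint) expected for the groups". The table row reads "Detectable Difference 0.46 0.34 0.23 0.11 0.05" mg/dL, for SDs of 1.00, 0.75, 0.50, 0.20 and 0.10. Each column has one SD, and the section does not say whether it belongs to the terlipressin group, the controls, or both pooled.

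Section 15.1 plans a mixed-effects regression "accounting for baseline SCr and the correlation structure between the repeated measures", together with a repeated-measures analysis of variance giving least-squares means. It mentions neither variances estimated by group nor robust standard errors.

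Three other places bear on the likely spread. Section 3.3 defines HRS reversal by an SCr of 1.5 mg/dL or less. Section 3.5.2 cites a trial stopped early for "considerable differences in HRS reversal between terlipressin and M&O (55.5 vs 4.8%, p<0.001". Section 6.1 describes the control group here as having had at least 48 hours of "treatment with Midodrine and Octreotide (M&O), albumin, or other vasopressor used for the treatment of HRS-AKI".

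**The concern.** In their usual form, both analyses in 15.1 estimate one between-patient variance and one residual variance for the two groups together. With 50 against 150 patients, that common estimate is dominated by the controls. If SCr change varies more on terlipressin, the standard error of the terlipressin coefficient comes out too small and its 95% interval too narrow.

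There is reason to expect such a difference. Reversal is a cut on SCr itself. If roughly half of one group responds and few of the other do, the first group mixes large falls with little change, while the second is mostly non-responders. The group expected to be the more mixed is also the one a third of the size, and that is the direction in which a common variance misleads. At stake is the stated precision of the study's main between-group estimate, and how 15.3 describes what the study can detect.

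**Working it through.** **Reproducing 15.3.** Inputs from 15.2 and 15.3: two-sided 0.05, 80% power, 50 and 150 patients, one SD.

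Detectable difference = SD × (1.960 + 0.842) × √(1/50 + 1/150) = SD × 2.802 × 0.1633 = 0.4575 × SD.

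| SD | 1.00 | 0.75 | 0.50 | 0.20 | 0.10 |
|---|---|---|---|---|---|
| Computed | 0.457 | 0.343 | 0.229 | 0.0915 | 0.046 |
| Printed | 0.46 | 0.34 | 0.23 | 0.11 | 0.05 |

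Four of the five columns reproduce, so the table rests on a common SD. The SD 0.20 column does not: about 0.09 follows, and the printed 0.11 would have 92% power. One-sided testing (0.08), equal allocation of 100 per group (0.08) and a t-based calculation (0.09) do not give 0.11 either.

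**Could the SDs differ?** The documents give no SD of SCr change for either group, so this step is assumption. Let responders and non-responders differ in mean change by D, with SD w within each. Then group variance = w² + p(1 − p)D². The cited rates give p(1 − p) = 0.555 × 0.445 = 0.247 for terlipressin and 0.048 × 0.952 = 0.046 for midodrine/octreotide.

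| D/w | 0.5 | 1 | 1.5 | 2 | 3 |
|---|---|---|---|---|---|
| SD ratio, terlipressin/control | 1.03 | 1.09 | 1.19 | 1.30 | 1.51 |

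This supports examining ratios up to about 1.5. It relies on equal spread within responders and non-responders. If the non-responder SD is k times the responder SD, with D measured in responder SDs, the group variances are equal when k² = 1 + (0.247 − 0.046)D²/(0.555 − 0.048) = 1 + 0.397D². That gives k = 1.18 at D = 1 and k = 1.61 at D = 2.

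**Effect on the interval.** Set the control SD to 1 and the terlipressin SD to r.

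- Common-variance SE² = [(49r² + 149)/198] × (1/50 + 1/150)
- True SE² = r²/50 + 1/150
- Coverage = probability that a standard normal lies within ±1.96 × (common-variance SE / true SE)

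At r = 1.3, the common-variance SE² is 1.1708 × 0.02667 = 0.0312 and the true SE² is 0.0338 + 0.0067 = 0.0405. The SE ratio is 0.878, and 1.96 × 0.878 = 1.72, so coverage is 91.5%.

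| r | 0.77 | 1.0 | 1.1 | 1.3 | 1.5 |
|---|---|---|---|---|---|
| Coverage of nominal 95% interval | 97.4% | 95.0% | 93.8% | 91.5% | 89.3% |

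These figures are for a simple two-group comparison of change. A simulation on assumed inputs (55.5% against 4.8% response, adjustment for enrolment SCr, 3,000 runs) gave 89.4% coverage with a common variance and 95.4% with robust standard errors. With 20% control response, the figures were 92.9% and 94.9%. A common-variance mixed model with random intercept and slope (213 fits, 55.5% against 4.8%) covered 91%. Adjustment therefore need not remove the effect, but its size in the planned model cannot be fixed from the documents.

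**Effect on the detectable difference.** Detectable difference = 2.8 × √(SD_T²/50 + SD_C²/150). With the control SD at 1.00:

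| r | 1.0 | 1.1 | 1.2 | 1.3 | 1.5 |
|---|---|---|---|---|---|
| Detectable difference | 0.46 | 0.49 | 0.53 | 0.56 | 0.64 |

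Power at the printed 0.46 × SD, with a valid standard error, depends on what the printed SD means:

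| Printed SD is that of | r = 1.1 | r = 1.3 | r = 1.5 |
|---|---|---|---|
| Controls | 74% | 62% | 52% |
| Both groups, pooled by size | 76% | 69% | 63% |
| Terlipressin group | 82% | 84% | 86% |

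**The case against.** A reader might infer that the cited response rates imply a larger SD on terlipressin, and hence that the printed 80% power is too high. The documents support neither step.

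- The rates are a binary outcome from another trial. Non-responders may vary more than responders: reversal compresses SCr to 1.5 mg/dL or below, section 3.1 describes rapid progression, and section 7.3 admits SCr up to 5.0 mg/dL, or higher with sponsor approval.
- The 4.8% is for midodrine/octreotide. These controls may have had albumin or another vasopressor, and at 20% control response the shortfall in coverage is small.
- The mechanism that widens the terlipressin SD also widens the mean difference. With responders falling by d, non-responders by 0 and other SD of 0.2d to 0.5d, the difference is (0.555 − 0.048)d = 0.507d. That is 1.9 to 3.0 times the detectable difference at the pooled SD, and power with a valid standard error exceeds 99%.
- If the printed SD is the terlipressin SD, power is 82% to 86%. The table is also a grid, so another column can be read.

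It is similarly tempting to infer an inflated false-positive rate. If the two groups have identical distributions, the 5% level holds. Within the mixture at 55.5% against 4.8%, the means cannot be equal. Only the coverage point remains.

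Three further replies have some weight. Section 15.1 is silent on variances rather than committed to equal ones. The between-group SCr comparison is listed as secondary in the synopsis and sections 5.1 and 13.2. The synopsis also describes the analysis as descriptive. Even so, 15.1 bases its primary model on the terlipressin association and 15.3 presents detectable differences for it, so that coefficient's interval should be valid. The objections lower the priority of the remedy without removing its value.

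**Conclusion.** The point stands as a cheap improvement to the analysis. As written, 15.1 leaves the interval for the terlipressin effect exposed if the two groups differ in spread. Under assumed SD ratios of 1.1 to 1.5, a nominal 95% interval covers about 94% to 89%. At a ratio of 0.77 it over-covers at 97.4% and gives away precision. A ratio above 1 is plausible from sections 3.3 and 3.5.2 but not established by them.

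Overstated power is a conditional matter only. It requires that the printed SD be the control or pooled SD and that the terlipressin SD be larger. Section 15.3 does not say whose SD it is, and that is the gap to close. The 0.11 at SD 0.20 is a separate arithmetic inconsistency.

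**What to change.** In 15.1, add a sentence pre-specifying either patient-clustered robust standard errors, or random-effect and residual variances estimated separately for terlipressin and control patients. Apply it to the terlipressin coefficient and to the least-squares-means contrast.

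In 15.3, state whose SD the table uses, and give detectable differences from 2.8 × √(SD_T²/50 + SD_C²/150) over SD ratios of about 1.0 to 1.5. For example, SD_T 0.90 and SD_C 0.60 give 2.8 × √(0.0162 + 0.0024) = 0.38 mg/dL. The pooled SD is √[(49 × 0.81 + 149 × 0.36)/198] = 0.69, for which the common-SD formula gives 0.31. Correct the SD 0.20 entry to about 0.09.

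The cost is one sentence, using standard options in the Stata software already named, and a revised table. No extra patients or data are needed. Intervals will be slightly wider and detectable differences less favourable if the terlipressin SD is the larger; if the variances are equal, the loss of efficiency is negligible.

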15.4 Safety Variables

Safety variables will include the following:

- Serious adverse events and all deaths. Safety details may include:
 - Vital signs (body temperature, blood pressure, heart rate, respiratory rate, and SpO₂).
 - MELD score.
 - Encephalopathy score.
 - Laboratory parameters.

Serious Adverse events will be not classified by Medical Dictionary for Drug Regulatory Activities (MedDRA) system organ class, preferred term, severity, and seriousness. SAEs will be summarized using site reported terminology, as well as by the investigator's assessment of the relationship of the SAE to the study drug.

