11.1 Vital Signs

Vital sign measurements will be recorded at baseline and daily during study drug administration. The measurements should be assessed and recorded at a consistent, specific time of day, preferable morning assessment/measurement.

Systolic and diastolic blood pressure, heart rate, body temperature, respiratory rate, and pulse oximetric saturation (SpO₂) will be recorded at baseline and during study drug administration.

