13.2 Secondary Efficacy Variables

- Improvement of renal function (SCr) from Day 1 through end of treatment, repeated measure analysis as compared to the Retrospective Control Group.
- For the Prospective Terlipressin Group alone and also in comparison to the Retrospective Control Group:
 - Incidence of dialysis by Day 30 and Day 90 of follow up.
 - Survival by Day 30 and Day 90 follow up.
 - Transplant by Day 30 and Day 90 follow up.
 - Serum creatinine at Day 30 and Day 90 follow up
 - Serum creatinine and incidence of dialysis at Day 30, Day 90, Day 180, and Day 365 after liver transplantation
 - Incidence of kidney transplant within one year after liver transplant
 - Descriptive analysis of number simultaneous liver kidney transplants and episodes of graft rejection at Day 90 and Day 365 after liver transplant

14 Serious Adverse Events

Only Serious Adverse Events will be collected for this study for the prospective group only. Safety review and assessments will be made only for the Prospective Terlipressin Group from time of first dose through 30 days after end of treatment. SAEs are collected from the start of study drug until 30 days after study drug was discontinued. Non-serious Adverse Events are not required to be collected for this study.

The investigator will record the nature, causality, severity, treatment, and outcome of the SAE, and will determine whether there is a “reasonable probability” that the study drug treatment caused the event.

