14.5 Study Drug Causality

Study drug causality will be assessed as follows:

Unrelated: An AE that is clearly and incontrovertibly due to extraneous causes (disease, environment, etc.) and does not meet the criteria for 'possible' or 'probable.'

Possible: The connection between the AE and study treatment appears unlikely but cannot be ruled out with certainty. An AE may be considered 'possibly related' if it has at least 2 of the following:

- It follows a reasonable temporal sequence from administration of study drug.
- It may readily have been produced by the subject's clinical state or by environmental or toxic factors.
- It follows a known response pattern to study drug.

Probable: An AE that is considered to be related to study drug treatment with a high degree of certainty. An AE may be considered probably related if:

- It follows a reasonable temporal sequence from administration of study drug.
- It cannot be reasonably explained by the known characteristics of the subject's clinical state.
- It follows a known pattern of response to study drug treatment.
- It reappears upon rechallenge.

Collaborative Research Study, Version 4: 06/29/21
To Treat HRS-AKI Patients with Continuous Terlipressin Infusion

Table 4 lists adverse events that are common in this subject population (i.e., with HRS), even in the absence of exposure to the study drug (Rozov-Ung and Panesar, 2010; Arroyo et al, 2008). The investigator may use this as a guidance while assessing the causality.

Table 4: Adverse Events Common to the Hepatorenal Syndrome (HRS) Population

MedDRA System Organ Class	Preferred Term
Blood and Lymphatic System Disorders	Anemia Coagulopathy
Cardiac Disorders	Atrial fibrillation Bradycardia
Gastrointestinal Disorders	Abdominal pain Diarrhea Nausea Vomiting
General Disorders and Administration Site Conditions	Multi-organ failure
Hepatobiliary Disorders	Hepatic failure
Infections and Infestations	Pneumonia Urinary tract infection
Metabolism and Nutrition Disorders	Hyperglycemia
Nervous System Disorders	Headache
Respiratory, Thoracic and Mediastinal Disorders	Dyspnea Epistaxis Pulmonary edema Respiratory failure
Vascular Disorders	Hypotension

Source: Rozov-Ung and Panesar, 2010; Arroyo et al, 2008.

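### SAEs, the only adverse events collected, are to be tabulated in the sites' own words with no stated rule for grouping synonyms, so term-level rates may be split and read too low

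*Combined protocol and SAP*

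**What the plan says.** Section 15.4 (Safety Variables) states: "Serious Adverse events will be not classified by Medical Dictionary for Drug Regulatory Activities (MedDRA) system organ class, preferred term, severity, and seriousness". It then gives the method to be used instead: "SAEs will be summarized using site reported terminology", with a further summary by the investigator's judgement of relatedness to the drug.

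The opening of section 14 limits what is collected: "Only Serious Adverse Events will be collected for this study for the prospective group only", and "Non-serious Adverse Events are not required to be collected for this study". The collection window runs from the first dose to 30 days after the drug is stopped. Section 14 also asks the investigator to record the severity of each SAE, and section 14.4 gives a three-level scale.

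SAEs are not the whole of the safety data. Section 15.4 opens its list with "Serious adverse events and all deaths. Safety details may include", followed by vital signs, MELD score, encephalopathy score and laboratory parameters. Sections 11.1 to 11.3, 12.2 and 12.3 schedule their collection; for example, "Vital sign measurements will be recorded at baseline and daily during study drug administration".

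Section 6.1 plans about 50 treated patients at 5-10 sites, and section 15.6 takes everyone with at least one dose as the safety population. No section gives a rule for combining differently worded reports of one event, or a list of events to be counted together.

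**The concern.** The primary objective in the Synopsis covers safety as well as efficacy, and the Synopsis and section 5.1 name SAEs up to 30 days after treatment as the safety assessment. Non-serious events are not required and SAEs are not collected for the retrospective controls. The SAE table therefore has no wider adverse-event table behind it and no control column beside it. Its event rates can be judged only against outside experience, which the protocol itself uses in sections 3.2 to 3.4 when it argues that infusion is better tolerated than bolus dosing.

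A table of free-text terms serves that purpose poorly. Several sites will report, and section 14.10 asks for complications such as variceal hemorrhage, encephalopathy, sepsis and pneumonia to be recorded as SAEs where applicable. Section 14.9 adds unplanned re-hospitalizations within 30 days of the end of treatment. These are events that different sites can readily describe in different words. If they do, one moderately common event can appear as several rare ones.

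The plan also handles similar data differently elsewhere. Section 15.5 reports medical conditions by body system, and section 14.12 foresees aggregate safety analyses for regulators, which need grouped events.

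**Working it through.** The plan states no SAE rate, so there is no figure of its own to reproduce. The check has two parts: a general result, and an illustration of size on assumed inputs.

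**General result.** Suppose one type of event is reported under k different wordings. Let A_j be the set of patients with wording j, and n the safety population.

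- Grouped rate = |A_1 ∪ … ∪ A_k| / n.
- Rate in row j = |A_j| / n.
- Since A_j is contained in the union, every row is less than or equal to the grouped rate. They are equal only if every affected patient has that wording.
- Adding the rows does not reliably recover the grouped rate, because a patient reported twice under two wordings is counted in both rows.
- The set of patients with any SAE, the deaths, and the SAE totals by relationship do not depend on wording, so they are unchanged.

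**Inputs for the illustration.** n = 50 (section 6.1). The number of wordings k and the true incidence p are not in the documents. They are assumed to be k = 2 to 4 and p = 5% to 20%, with one wording per affected patient.

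**Single example.** Five patients have one event under three wordings, split 2/2/1. The exact (Clopper-Pearson) 95% intervals are:

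| Row | Patients | Rate | 95% CI |
|---|---|---|---|
| Grouped | 5/50 | 10% | 3.3-21.8% |
| Wording A | 2/50 | 4% | 0.5-13.7% |
| Wording B | 2/50 | 4% | 0.5-13.7% |
| Wording C | 1/50 | 2% | 0.1-10.6% |

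**Even split.** Largest row = ceil(x/k)/50 for x affected patients. For x = 5 (10% grouped), the largest row is 6%, 4% and 4% for k = 2, 3 and 4. For x = 10 (20% grouped), it is 10%, 8% and 6%.

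**Random wording.** X ~ Binomial(50, p), each affected patient assigned one of k wordings with equal chance, 200,000 simulated trials. Expected largest row:

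| True rate | k = 2 | k = 3 | k = 4 |
|---|---|---|---|
| 5% | 3.7% | 3.2% | 2.9% |
| 10% | 6.7% | 5.5% | 4.9% |
| 20% | 12.5% | 9.8% | 8.4% |

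As a share of the true rate, this runs from 8.37/20 = 42% to 3.7/5 = 74%. With p = 10% and k = 3, the chance that some single row shows three or more patients is 56%, against 89% when the wordings are grouped.

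**The case against.** The strongest reply is that the choice is disclosed, the study is small and open-label, and there is no SAE comparison with controls, so no between-group estimate is biased. All SAE forms go to one safety review officer within 24 hours (section 14.12), a reader can group the SAEs of about 50 patients from a listing, and the Synopsis allows further sponsor analyses. Section 14.12 also cites a safety review plan, which is not among the documents; a grouping rule there cannot be ruled out. These points lower the stakes. They do not replace the tabulation rule that section 15.4 actually states, and none of them commits anyone to grouping.

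Four stronger readings are tempting and are not supported.

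- **That SAEs are the only safety data.** They are the only adverse events. Deaths are also a named safety variable, and vital signs, encephalopathy, MELD and laboratory data are scheduled.
- **That rates will be understated.** This depends on sites using different words, which the documents do not show. Only term-level rows are exposed.
- **That Table 4 ("Adverse Events Common to the Hepatorenal Syndrome (HRS) Population") is a reference list that the SAE results cannot be matched to.** Section 14.5 offers it as optional guidance for judging causality case by case. Its terms are ordinary clinical words, and no matching of tabulated SAEs to it is planned.
- **That severity is barred from the report.** Section 15.4 says SAEs will not be classified by severity, but the sentence lists severity and seriousness as if they were MedDRA levels. It is ambiguous about listings, and severity is recorded in any case.

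For cardiac and mesenteric ischemia there may be a second route to the count: the Synopsis ties these events to stopping the drug, and section 15.5 summarises reasons for discontinuation. It does not define the categories, so this is a partial safeguard only.

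**Conclusion.** The concern stands as a weakness in the planned SAE table. Section 15.4 commits to uncoded site terms, and no section supplies a rule for synonyms. Where wordings differ, the per-term rate is never higher than the grouped rate and may be well below it. On the assumed ranges (true incidence 5-20%, two to four wordings chosen equally at random, 50 patients), the largest single row would be expected to show about 42-74% of the true rate. The direction follows from counting alone; the size rests wholly on those assumptions, since the documents give neither SAE rates nor the number of wordings. The any-SAE proportion, deaths and totals by relationship are unaffected, and no comparison with the control group is involved. The change is worth making because the SAE table is the plan's only adverse-event output, and the remedy needs no new patient data.

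**What to change.** Amend section 15.4 so that:

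1. Each SAE is assigned a MedDRA preferred term and system organ class. At minimum, verbatim terms are grouped centrally under a rule written before the analysis.
2. The verbatim term is kept beside the assigned term in the listings, so that the grouping can be checked.
3. The tables give the number and percentage of patients in the safety population with at least one event, by group, by the severity already recorded, and by relatedness.
4. If the safety review plan already holds a grouping rule, section 15.4 cites it and uses it for the tables.

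The cost is a protocol amendment and a small amount of coding work on the SAEs of about 50 patients. The documents do not say how many SAEs to expect or who would code them. The forms already reach one safety review officer, and coding can be done after collection.
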